6.8 Pharmacodynamic Assessment

Urinary glucose excretion (UGE) will be determined as the PD parameter. Urinary creatinine will be determined to calculate the creatinine normalized UGE.

6.9 Adverse Events Assessments

Adverse event (AE): Any untoward medical occurrence in clinical investigation subject administered a pharmaceutical product. An AE does not necessarily have to have a causal relationship with this treatment.

Serious adverse event (SAE): A serious adverse event (experience) or reaction is any untoward medical occurrence that at any dose:

- results in death,
- is life-threatening (NOTE: The term "life-threatening" in the definition of "serious" refers to an event in which the patient was at risk of death at the time of the event and does not refer to an event which hypothetically might have caused death if it were more severe.),
- requires inpatient hospitalization or prolongation of existing hospitalization,
- results in persistent or significant disability/incapacity,
- is a congenital anomaly/birth defect,
- is an important medical event.

An important medical event is an event that may not be immediately life-threatening or result in death or hospitalization but may jeopardize the patient or may require intervention to

prevent one of the other outcomes listed in the definition above. Examples of such events are intensive treatment in an emergency room or at home for allergic bronchospasm, blood dyscrasias or convulsions that do not result in hospitalization, or development of drug dependency or drug abuse.

Non-serious adverse events are all events that do not meet the criteria for a "serious" adverse event.

Immediately Reportable Adverse Event (IRAE): Any serious adverse event or any adverse event that necessitates discontinuation of investigational product.

Clinical Laboratory Changes: It is the investigator's responsibility to review the results of all laboratory tests as they become available. For each abnormal laboratory test result, the investigator needs to ascertain if this is a clinically significant change from baseline for that individual subject. This determination, however, does not necessarily need to be made the first time an abnormal value is observed. The investigator may repeat the laboratory test or request additional tests to verify the results of the original laboratory tests. If this laboratory value is determined to be an abnormal change from baseline for that subject, this is considered an AE.

Hypoglycemia will be defined as any fasting plasma glucose (FPG) value < 70 mg/dL and documented as described in [Section 6.9.4.4](#).

Any increase in liver function tests (AST, ALT, or bilirubin) greater than 3 times the upper limit of normal (ULN) for the laboratory utilized will be considered a clinical laboratory adverse event.

An increase in creatinine from baseline by 0.5 mg/dL or more will be reported as a laboratory adverse event.

Severity: Adverse events will be graded on a 3-point scale and reported as indicated on the CRF. The intensity of an adverse experience is defined as follows:

1 = Mild: discomfort noticed, but no disruption to daily activity

2 = Moderate: discomfort sufficient to reduce or affect normal daily activity

3 = Severe: inability to work or perform normal daily activity

Investigational Product Causality: The site and database should ask for the causality relative to the study compound. Relationship of an adverse event to dosing will be assessed as follows:

Definite: There is a reasonable causal relationship between the investigational product and the AE when the event responds to withdrawal of the investigational product (dechallenge), and recurs with administration of the investigational product (rechallenge).

Probable: There is a reasonable causal relationship between the investigational product and the AE. The event responds to dechallenge. Rechallenge is not required.

Possible: There is a reasonable causal relationship between the investigational product and the AE. Dechallenge is lacking or unclear.

Not Likely: There is a temporal relationship to investigational product administration, but there is not a reasonable causal relationship between the investigational product and the event.

Unrelated: There is no temporal or causal relationship to investigational product administration.

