5 STUDY TREATMENT(S)

5.1 Description of Treatment(s)

5.1.1 Study Drug

Bexagliflozin tablets, 20 mg, are blue caplet-shaped, film-coated tablets that are intended for use in investigational studies in humans. The tablets contain excipients designed to promote extended release through a gastroretentive mechanism. The active tablets exhibit a greater than 75% release of drug substance by 8 hours in simulated gastric fluid *in vitro*.

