5.9 Packaging and Labeling

5.9.1 Bexagliflozin

Bexagliflozin tablets, 20 mg, are packaged in high density polyethylene bottles sealed with a child resistant closure. The product is packaged with 90 tablets per bottle.

Investigational product bottles will be labeled with protocol number, drug name and strength, lot number, sponsor's name, storage condition, and the investigational drug caution statement.

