9.7.1 Adverse Events

Adverse events will be mapped to preferred term and body system using the Medical Dictionary for Regulatory Activities (MedDRA). In treatment period 1, 10 subjects in group 1 will receive a single oral dose of 20 mg bexagliflozin and in treatment period 2 another 10 subjects will receive the same dosing. As a result, a total of 20 subjects will receive a single oral dose of bexagliflozin alone. Likewise, a total of 20 subjects will receive a co-administration of bexagliflozin and exenatide. The number and percentage of subjects

reporting adverse events will be determined by relationship to dosing and by severity of the event. Drug-related adverse events will be considered those to be at least possibly related to bexagliflozin and/or exenatide administration.

Adverse event listings will be provided for the following subsets:

- all treatment emergent AEs (TEAEs)
- all TEAEs at least possibly related to bexagliflozin or exenatide
- serious TEAEs (if any)
- TEAEs leading to study discontinuation (if any).

AEs are treatment emergent if they occur on or after bexagliflozin and/or exenatide administration. TEAEs will be considered at least possibly related to bexagliflozin or exenatide based on the investigator's assessment. Only TEAEs will be tabulated in summary tables. If the AE(s) onset date-time or date occurs after the first dose up until right before the next dose, the AE(s) will be assigned to the first treatment. Any AE(s) that occur after the second dose up until the follow-up visit will be assigned to the second treatment. Tabulations will display TEAEs by severity and relationship to bexagliflozin and/or exenatide.

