6.3.3 Adverse Events (AEs)

Adverse events will be collected and coded using version 20.0 (or newer) of MedDRA. Analysis of adverse events will be carried out on the Safety Population. All adverse events will be included in the individual subject data listings. Only treatment emergent adverse events (TEAEs) will be tabulated in summary tables. The incidence of TEAEs will be presented by treatment. If the AE(s) onset date-time or date occurs after the first dose up until right before the second dose, the AE(s) will be assigned to the first treatment. If the AE(s) onset date-time or date occurs after the second dose, the AE(s) will be assigned to the second treatment.

All adverse events will be assessed by the investigator(s) with respect to severity, relationship to study drug and seriousness.

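### Causality is graded once, against an undefined study compound, while the protocol's related-event outputs need relatedness to bexagliflozin and/or exenatide

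*Protocol*

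**What the plan says.** **Collection.** Under the causality heading in Protocol 6.9, "The site and database should ask for the causality relative to the study compound". The next sentence is worded differently: "Relationship of an adverse event to dosing will be assessed as follows". The five grades that follow (Definite, Probable, Possible, Not Likely, Unrelated) all return to a single investigational product. Not Likely, for example, requires a temporal relationship but says "there is not a reasonable causal relationship between the investigational product and the event". Neither the compound nor the product is defined in that section.

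SAP 6.3.3 states: "All adverse events will be assessed by the investigator(s) with respect to severity, relationship to study drug and seriousness". SAP 6.3.3.6 speaks of relationship to dosing and refers back to the criteria in Protocol 6.9. The fourth counting rule in SAP 6.3.3.4 also assumes one relationship per event.

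**Analysis.** Protocol 9.7.1 defines drug-related events by reference to either drug and takes the call from the investigator: "TEAEs will be considered at least possibly related to bexagliflozin or exenatide". It requires a listing of those events and tabulations by relationship to one or both drugs.

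**Grouping.** The SAP glossary entry for treatment related (TR) takes in four grades, Not Likely among them, and leaves only Unrelated outside. SAP 8.4.1 counts a missing relationship as related.

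**The concern.** The analysis calls for a judgement about two drugs, but the collection instruction asks about one unnamed compound. An investigator who puts nausea after the injection down to exenatide has no stated rule for answering. Protocol 1.2 names nausea, vomiting and diarrhoea as the most common events with this drug class, so the case is foreseeable.

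Exenatide is given only in the combination period, so the ambiguity is one-sided. In the bexagliflozin-alone period the compound, the product and the dosing are all the same thing. In the combination period they may differ. A difference between treatments in related events could then partly reflect how the question was read. The secondary objective is the safety and tolerability of bexagliflozin given with exenatide, and the related-event listing and tabulations are part of the evidence for it.

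**Working it through.** No figure in the plan bears on this point, so the check is a comparison of texts.

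**Step 1: what the singular term most naturally means.** The heading "5.1.1 Study Drug" covers bexagliflozin alone ("Bexagliflozin tablets, 20 mg, are blue caplet-shaped, film-coated tablets that are intended for use in investigational studies in humans"), and exenatide has its own heading, 5.1.2. Protocol 5.9.1, on bexagliflozin packaging, says "Investigational product bottles will be labeled with protocol number, drug name and strength"; 5.9.2, on exenatide, does not use that term. The synopsis classes exenatide as reference therapy. These places point to bexagliflozin (reading A).

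**Step 2: what supports a wider meaning.** Protocol 6.9 and 9.7.1 and SAP 6.3.3.6 also speak of relationship to dosing, and dosing in the combination period includes exenatide. Protocol 6.10 treats any medicine other than the investigational product as concomitant; on reading A that would make the assigned exenatide a concomitant medication. SAP 6.3.2 covers both drugs under study medication. So a combined meaning (reading B: any study dosing) is also open.

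**Step 3: follow an event in the combination period through each reading.** The protocol set is at least Possible (9.7.1). The SAP set is the glossary's treatment-related group.

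| Investigator's opinion | Reading A: bexagliflozin only | Reading B: any dosing |
|---|---|---|
| Due to bexagliflozin | In both sets | In both sets; drug not identified |
| Due to exenatide, onset after the tablet | Not Likely: outside the protocol set, inside the SAP set | In both sets; drug not identified |
| Due to exenatide, onset in the 30 minutes between injection and tablet | Unrelated, since it precedes bexagliflozin: outside both sets | In both sets; drug not identified |
| Due to neither, but close in time | Not Likely: outside the protocol set, inside the SAP set | Not Likely: outside the protocol set, inside the SAP set |

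On reading A the 9.7.1 output for either drug cannot be derived from the collected grade. On reading B it can be derived, but the grade does not show which drug was meant. The Not Likely rows show that the protocol and the SAP glossary disagree whichever reading is taken.

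**Step 4: which outputs are exposed.** The 9.7.1 related-event listing and tabulations depend on the grade. Overall event incidence by treatment (SAP 6.3.3 and 8.4.1) does not, and all events are listed whatever their cause. The three summaries named in SAP 8.4.1 include no table by relationship, although its missing-data rule refers to related tables. SAP section 10 records no departure from 9.7.1, so the protocol's outputs still stand.

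**Step 5: scale.** Protocol 9.7.1 plans 20 subjects on the combination. Each subject whose only related event changes status moves the combination-period percentage by 1/20 = 5 percentage points. The documents give no incidence of exenatide-attributed events, so the number of such subjects, and hence the total shift, is unknown.

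**The case against.** The best counter-argument is that the documents can be read together sensibly. Relationship is to dosing, dosing includes exenatide, and 9.7.1 says the investigator's assessment covers either drug. A single item meets an and/or definition if it is understood that way, and one clarifying sentence would settle it. Moreover, the injection and the tablet are 30 minutes apart on a single day, and the scale leans on dechallenge and rechallenge, so separate grades per drug may not be reliable.

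Much of this stands. Reading B is available, and attribution by drug will be imprecise. But the grades themselves go back to a singular product, so the text supports two answers to one question. A clarifying sentence in favour of reading B would make the 9.7.1 set derivable but would still leave each event unattributed.

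A reader might go further and infer three things that the documents do not support:

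- *That exenatide-caused events are scored as not related.* No section says so. It follows only on reading A with the protocol's cut-off. Under the SAP glossary a Not Likely event counts as treatment related, and an event starting after the tablet would usually be temporally linked to both drugs.
- *That the database has no field for exenatide.* The SAP cites an annotated CRF dated 12-JUN-2017 that is not among the documents, so this cannot be checked.
- *That the combination treatment's related-event rate shifts by a particular amount.* Any such figure needs an assumed incidence that the documents do not give.

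**Conclusion.** The mismatch between collection and analysis is real and worth correcting. Under the narrower and more natural meaning, exenatide-attributed events in the combination period may drop out of the protocol's related-event listing and tabulations. Under the wider meaning they stay in, but relatedness cannot be attributed to a drug. Separately, the protocol and the SAP glossary place Not Likely on opposite sides of the related/not-related line.

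The reach is limited to related-event outputs for a secondary objective, and the primary PK/PD analyses do not use causality. The size cannot be stated from the documents. The conclusion rests on the protocol and SAP wording alone; if the CRF already asks about each drug separately, only the text and the glossary need aligning.

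**What to change.** 1. In Protocol 6.9, the CRF and SAP 6.3.3 and 6.3.3.6, record causality on the existing five-point scale separately for bexagliflozin and, in the combination period, for exenatide. Word the grades so that each refers to the named drug.
2. In Protocol 9.7.1 and the SAP, define drug-related as at least Possible on either grade, and show relatedness to each drug by treatment.
3. Change the SAP glossary's treatment-related and not-treatment-related entries so that Not Likely falls on the same side as in the protocol.

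The cost is one added CRF field, short text edits and slightly more recording per event. Because the two doses are so close together, the per-drug grades should be reported as the investigator's opinion and not as firm attribution. The change is best made before data collection, since a judgement not recorded at the time could be obtained only retrospectively.

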6.9.1 Collecting and Reporting Adverse Events

The investigator or designee will periodically assess subjects for the occurrence of adverse events. To avoid bias in collecting information about adverse events, the investigator or designee should ask subjects the following question: "How have you felt since you were last checked?" All adverse events (serious and non-serious) reported by the subject must be recorded on the source documents and CRFs provided by the sponsor.

In addition, Theracos' Medical Monitor or its designated personnel must be notified immediately by telephone or fax of any immediately reportable adverse events according to the procedure outlined below. Special attention should be paid to recording hospitalization and concomitant medications.

6.9.2 Immediately Reportable Adverse Events

The investigator or designee must report any serious adverse event (SAE), by telephone, email, or fax, to Theracos or its representative immediately after the investigator or study staff becomes aware of the event. An immediately reportable adverse event (IRAE) form should be completed and sent by email or fax or overnight courier to the sponsor within 24 h of knowledge of the event.

Non-serious events that require discontinuation of investigational product (including laboratory abnormalities) should be reported to Theracos within 3 working days. The IRAE form should be completed and sent by email or fax or overnight courier to the sponsor.

Subjects experiencing an SAE should be followed clinically until their health has returned to baseline status or until all parameters have returned to normal, or have otherwise been explained. It is expected that the investigator will provide or arrange appropriate supportive care for the subject.

6.9.3 Pregnancy

Women of childbearing potential (WOCBP) who are sexually active must use an effective method of birth control during the course of the study, in a manner such that risk of failure is minimized.

Before enrolling WOCBP in this clinical trial, investigators must review guidelines about study participation for WOCBP. The topics should generally include:

1. General information.
2. Informed consent form.
3. Pregnancy prevention information.
4. Drug interactions with hormonal contraceptives.
5. Contraceptives in current use.
6. Guidelines for the follow-up of a reported pregnancy.

Prior to study enrollment, WOCBP must be advised of the importance of avoiding pregnancy during trial participation and the potential risk factors for an unintentional pregnancy. The subject must sign an informed consent form stating the above-mentioned risk factors and that the consequences were discussed with her.

During the study, all WOCBP should be instructed to contact the investigator or designated study staff immediately if they suspect they might be pregnant (e.g., missed or late menstrual cycle).

If a subject, investigator or designee suspects that the subject may be pregnant prior to investigational product administration, the investigational product administration must be withheld until the results of serum pregnancy tests are available. If the pregnancy is confirmed, the subject must not receive the investigational product and must not remain in or be enrolled in the study.

The investigator or designee must notify the Medical Monitor within 3 working days of the receipt of information that any female subject who has become pregnant.

The investigator or designee must record the event on the Pregnancy Surveillance form and forward it to the sponsor's clinical or designated personnel.

6.9.4 Follow-up of Adverse Events

6.9.4.1 Follow-up of Non-serious Adverse Events

Non-serious adverse events that are identified on the last scheduled contact must be recorded on the AE CRF with the current status noted. All non-serious events that are ongoing at the time will be recorded as ongoing on the CRF.

6.9.4.2 Follow-up of Post-Study Serious Adverse Events

SAEs that are identified on the last scheduled contact must be recorded on the AE CRF page and reported to Theracos according to the reporting procedures outlined in [Section 6.9.1](#). These may include unresolved previously reported SAEs, or new SAEs. The investigator or designee should follow these subjects until the events are resolved, or the subject is lost to follow-up. Resolution means the subject has returned to the baseline state of health, or the investigator does not expect any further improvement or worsening of the subject's condition. The investigator or designee should continue to report any significant follow-up information to Theracos until the event has been resolved.

Any new SAEs reported by the subject to the investigator that occur after the last scheduled contact, and are determined by the investigator to be reasonably associated with the use of the investigational product, should be reported to the Medical Monitor or the sponsor's designated personnel. These may include SAEs that are captured on follow-up telephone contact or at any other time point after the defined study period (i.e., up to last scheduled contact). The investigator or designee should follow subjects with SAEs identified after the last scheduled contact until the events are resolved, or the subject is lost to follow-up. The investigator or designee should continue to report any significant follow-up information to the Sponsor until the event has been resolved.

6.9.4.3 Hepatotoxicity

Any clinically significant increase in hepatic enzymes and specifically ALT or AST $\geq 3x$ ULN requires immediate repeat test within 48 to 72 h to confirm the hepatic enzyme elevation. Study medication should be stopped and the event should be reported as an adverse event within the CRF if the enzyme elevation is confirmed or worsening. Potential contributors to hepatic enzyme elevation should be evaluated by the investigator. The investigator is encouraged to consult with the Medical Monitor regarding ongoing diagnostic workup.

Investigational product should be permanently discontinued if any of the following criteria is met:

- ALT or AST $> 8xULN$,
- ALT or AST $> 3xULN$ and (total bilirubin $> 2xULN$ or INR > 1.5),
- ALT or AST $> 3xULN$ with the appearance of fatigue, nausea, vomiting, right upper quadrant pain or tenderness, fever, rash, and/or eosinophilia ($> 5\%$).

6.9.4.4 Hypoglycemia

Hypoglycemia will be recorded under 5 categories:

- Critical hypoglycemia: An event requiring assistance of another person to actively administer carbohydrate, glucagons, or other resuscitative actions. These episodes may be associated with sufficient neuroglycopenia to induce seizure or coma. Plasma glucose

measurements may not be available during such an event, but neurological recovery attributable to the restoration of plasma glucose to normal is considered sufficient evidence that the event was induced by a low plasma glucose concentration. All such events should be recorded as serious adverse events in the CRF.

- Documented symptomatic hypoglycemia: An event during which typical symptoms of hypoglycemia are accompanied by a measured plasma glucose concentration ≤ 70 mg/dL (3.9 mmol/L).
- Asymptomatic hypoglycemia: An event not accompanied by typical symptoms of hypoglycemia but with a measured plasma glucose concentration ≤ 70 mg/dL (3.9 mmol/L).
- Probable symptomatic hypoglycemia: An event during which symptoms of hypoglycemia are not accompanied by a plasma glucose determination but that was presumably caused by a plasma glucose concentration ≤ 70 mg/dL (3.9 mmol/L).
- Relative hypoglycemia: An event during which the subjects report any of the typical symptoms of hypoglycemia, and interprets those as indicative of hypoglycemia, but with a measured plasma glucose concentration > 70 mg/dL (3.9 mmol/L).

If a subject experiences symptomatic hypoglycemia, confirmed by point-of-care glucose monitoring at the time of symptoms with a blood sugar level < 70 mg/dL (3.9 mmol/L), the subject should be treated with 15 to 20 grams of oral glucose or simple carbohydrate (glucose tablets, raisins, orange juice, glucose-containing soda, or soft sugar candies).

If a subject with symptomatic hypoglycemia is unable to self-administer glucose tablets, candies, or glucose-containing solutions, then the appropriate study staff should administer either intramuscularly or subcutaneously a single injection of 1.0 mg of glucagon. A single dose of glucagon should restore consciousness within approximately fifteen minutes. Failure to correct hypoglycemia within this timeframe or observation by appropriate study staff of profound low sugar with accompanying coma or seizure will be treated by intravenous infusion of 5% dextrose.

Blood glucose monitoring will be done by appropriate study staff using a point-of-care glucose monitor beginning at the time of hypoglycemia detection and continue every fifteen minutes, or more frequently if required, until that time that the subject's level of alertness has returned to appropriate levels and point-of-care glucose levels are above 70 mg/dL.

